### 5.5 Study Evaluations

a. Veteran participants (Aims 1 and 2)  
Per IRB-approved procedures, this study involved several assessment components: initial phone screen to ascertain interest and basic

inclusion/exclusion eligibility, eligibility confirmation, consent and enrollment, baseline assessment, 16-week satisfaction questionnaire, and 6-and 12-month follow-up outcome assessments.

**Table 5. Quantitative Measures for RCT: Covariates, and Aim 1 and 2 Outcomes**

Domain	Measure
Baseline Covariates Associated with Weight or PTSD (will be adjusted in a weight or b PTSD analyses)	
African-American race/ethnicity a	Self-reported African-American race/ethnicity 
Aim 1: Test MOVE!+UP's Effects on Weight (Primary) and PTSD (Secondary) Outcomes	
Primary outcome: weight loss	Standardized protocol and equipment at baseline and 6 months. Will also explore 12-month weight loss in secondary analyses.
Secondary outcome: PTSD symptoms	PTSD Checklist for DSM-5  PTSD symptomology will be recorded at baseline, 6 months, and 12 months.
Aim 2: Exploratory Changes on Treatment Targets from Baseline to 6 months	
Diet quality and eating habits	Starting the Conversation  and PACE eating habits measure
Night eating	Night Eating Questionnaire 
Emotional eating	Emotional Overeating Questionnaire 
Binge eating with purging vs binge eating without purging vs no binge eating	PHQ-15  modified to reflect DSM-5 changes plus items from PACE eating habits
Two outcomes: Average physical activity (light, moderate, and vigorous; moderate and vigorous)	Actigraph accelerometers, gold standard 
Social support	Helpful and unhelpful behaviors from others for activity/diet 
Insomnia severity	Insomnia Severity Index 
Depression symptoms	PHQ-8 
Internalized Weight Bias	Modified Weight Bias Internalization Scale

**Phone screen (5-20 minutes; see ALT Phone Screen).**

Study personnel provide an overview of the study and, for those still interested, conducted an initial pre-consent screening, which consists of questions corresponding to inclusion criteria/exclusion. To proceed to the in-person eligibility assessment phase, the potential participant must 1) be age 18 or older, (2) be a Veteran of the US military, (3) be a VA Puget Sound patient, (4) screen positive on the 4-item Primary Care PTSD Screen (PC-PTSD) as a likely indication of PTSD, (5) report a BMI that is classified as obese or as overweight, (6) be enrolled in PTSD care, (7) be motivated and willing to participate in all intervention or control and assessment activities, (8) be fluent in English, (9) have telephone access, and (10) receive VA primary care provider approval. The potential

participant must also deny (1) severe hearing loss, (2) being pregnant, (3) current participation in *MOVE!*, and (4) past year bariatric surgery or planned for the coming 6 months. We also assessed if the potential participant can safely weigh themselves at home using a study-provided scale. Should they be unable to weigh themselves safely at home using the mailed study scale during the virtual eligibility assessment visit (e.g., they are fully wheelchair-bound), they were considered ineligible, as we had no means of safely weighing them in person using a wheelchair-accessible scale. In addition, veterans were excluded during the phone screening if they report that they have a baseline weight >440 lbs.

We also assessed access to VVC enabled technology, secure messaging, and permission to email materials (and instructions for that process if used via one-way email from study staff to participants, using the already IRB-approved text scripts to craft messages; see Telehealth Team Guidance Outlook email).

The purpose of the pre-consent eligibility screening was to quickly determine which candidates are most likely to qualify, thus eliminating the need to conduct consent and full eligibility assessments for all potential participants. If potential participants are found to likely be eligible following the pre-consent eligibility screening, the study coordinator scheduled the virtual eligibility and baseline assessment visit, which was conducted virtually, ideally via VVC (but via phone if preferred or Veteran cannot or does not want to use VVC or other approved video conferencing modality should VVC not be working), allowing adequate time for study materials (and CVT connect program equipment to be mailed to participants who need it for VVC sessions and assessments).

The following also occurred:

a) Participants who did not have an internet-enabled tablet or computer from which they can join study visits and intervention sessions were sent one through the CVT connect program by study staff placing a consult in their chart, using standard procedures.

b) Participants were mailed several study materials, including the study-provided scale; the Information Statement; orientation materials and the group VVC Telehealth agreement (discussed further below, see ALT Orientation Script & Materials and ALT Group VVC Telehealth Agreement); a hard copy of the baseline measures (see Baseline Assessment) accelerometer and accelerometer instructions and the hard copy logs (see Activity Monitor Instructions and Activity Monitor Daily Tracking Log and Daily Food Beverage & Activity Log); and a postage-paid envelope for returning the accelerometer to the study team.

If a subject preferred to receive the materials in person, rather than by having USPS/UPS deliver study materials to their home (or being unable to receive USPS/UPS deliveries), study staff offered to meet with the Veteran in-person at the VA in a clinical setting for a face-to-face visit in order to hand off the materials. All VA policies with regard to masking and

distancing during the SARS-CoV-2 pandemic were followed during this interaction. This option was also offered to enrolled study subjects for all follow-up assessments and visits. Staff were sure to confirm identity of the participant prior to interacting and did so in a private location to protect the identity of the individual.

c) Study staff confirmed approval with Veteran's PCP or other physician for participation following the screening and eligibility visit, so it was possible someone's physician could disallow participation after they've provided verbal consent to participate in the study (see ALT PCP Approval Template). If the potential participant was scheduled for an assessment less than seven days after they completed the phone screen, or if the participant was scheduled to be assessed within 48 hours but the approval had not been received, study staff sent an email to the PCP or other physician (see ALT PCP Email template). For Veterans who did not have a PCP but who are established with another physician for care (e.g., psychiatry), we sought that physician's approval using the same procedures used for PCP approval.

We had IRB approval to allow potential participants to participate in *MOVE!+UP* who didn't have VA PCPs or other physician. In those cases, we would obtain community PCP approval of *MOVE!+UP* participation using the standard PCP approval template, obtained through fax or other secure means after a release is signed by the participant. The PCP approval template would be entered into CPRS with [name] as the signer and a note at the top of the CPRS note saying "this is for Veteran's outside VA PCP to review." This note would be sent to the participant by study staff after obtaining the ROI to take it to their PCP for PCP signature and returned to study staff by mail or using secure messaging.

**Eligibility assessment (15-30 minutes; see ALT Eligibility Measures).**

The follow-up eligibility assessment was conducted virtually, ideally by VVC, at a time that allowed study materials to have been mailed to the participant. The various components of the assessment visit can be completed on different dates as needed (as long as all components are completed within the acceptable assessment visit window) to best accommodate Veterans. Ideally, all components would be completed on the same day during the same VVC visit.

Prior to the visit, study staff confirmed receipt of mailed materials and the study scale and would troubleshoot any issues with VVC connection. Should VVC be having issues, staff would send the participant a link, via one-way text or email to the participant, to another approved video conferencing modality from which they could join the assessment visit (see Text Scripts).

Study participants were asked to weigh themselves with the study-provided scale to confirm they meet the eligibility criteria for the study (overweight/obese status; BMI of at least 25). Height for BMI calculation was based on CPRS-based information.

They also completed a current assessment of PTSD symptoms, administered by study staff. Current PTSD was confirmed during this visit as indicated by endorsing at least one lifetime traumatic event on the Life Events Checklist for DSM-5 (LEC-5) and based on their score on the PTSD Checklist for DSM-5 (PCL-5). A provisional PTSD diagnosis can be made by following the DSM-5 diagnostic rule, which requires at least moderate severity endorsement (a score of at least 2) on the following: 1 B item (questions 1-5), 1 C item (questions 6-7), 2 D items (questions 8-14), and 2 E items (questions 15-20). In addition, to meet PTSD diagnosis criteria, the individual must obtain a score of  $\geq 33$  on the PCL-5. As long as they continue to meet those inclusion criteria, they may be officially enrolled in the study and designated for randomization.

Respondents who do not meet eligibility criteria were offered a resource list (see Mental Health Resources Handout), and given *MOVE!* contact information and told to follow-up with their primary care provider or mental health treatment coordinator for mental health treatment or other care coordination needs.

For those who were eligible, we collected contact information (e.g., address, telephone number, and whether they provide permission for us to text reminders to a mobile telephone number) and contact information for at least one friend or family member who typically would know the whereabouts of the participant should study staff have difficulty making contact will be recorded. Eligible patients were invited to learn more about the study, and proceed with orientation (process described below) and verbal consent (process described in **Section 5.3.a. Informed Consent Procedures**). After providing verbal consent to proceed with enrollment, they completed baseline measures, and be randomized to either *MOVE!* (control) or *MOVE!+UP* (intervention).

**Orientation content (10-15 minutes; see ALT Orientation Script & Materials).** Study staff spent 10-15 minutes during the enrollment session prior to reviewing the consent orienting participants to the process of research participation and the importance of accepting randomization group and following through with follow-up assessments, using the mailed orientation materials. This is to better outline study activity expectations, including the total amount of time expected in weekly activities for the program and study. We also offered an opportunity for participants to consider the pros and cons of participation, a standard motivational interviewing technique. They also were asked to consider whether they can make two personal commitments: 1) to working on their health and weight and 2) to participate in the study procedures. Because this conversation took place during the virtual enrollment visit, it was not used to attract people to the study but rather to fully inform them about all involved in participation, including randomization into the control versus the intervention group, therefore enhancing the informed consent process (i.e., this process was not trying to unduly influence people to enroll in the study, rather give them more opportunity to consider NOT enrolling if they

don't think they can follow through with the study's expectations). Materials and plans are based on a model found to be very successful in other interventions facing difficult retention situations, and used in our pilot work. Participants then proceeded to informed consent (detailed process described in **Section 5.3.a. Informed Consent Procedures**). After providing verbal consent to enroll in the study, they proceeded to complete baseline measures. They were then randomized, and notified of their assignment and details/logistics, and reminded that materials would be mailed to them for their program (*MOVE!+UP* or *MOVE!*).

**Exploratory measures, accelerometer, and logs (45 minutes).** To ensure that all exploratory behavioral and psychological measures were collected prior to randomization, study staff administered the questionnaire during the virtual visit, starting with cohort 2 (prior to that, participants were able to complete it on their own and mail it back, leading to some lost baseline questionnaires). Administering the questionnaire in real-time helped ensure the data were collected in a timely and reliable manner.

Participants were asked to wear an accelerometer and complete associated logs (see Activity Monitor Daily Tracking Log and Daily Food Beverage & Activity Log) for one week following the baseline visit. Participants received a reminder mid-week to complete the logs, and at the end of the week to return them in the pre-addressed, pre-paid envelope. Study staff reminded the participant to remove the accelerometer and facilitated expedited return via UPS. If accelerometer data were invalid upon return (e.g., empty data) or not returned, we occasionally asked a participant—but did not require—to re-wear an accelerometer. If the accelerometer and logs had not been returned one week after the participant was scheduled to take it off, study staff would call or text the participant to remind them to return it. If it still had not been returned after another 3-5 days, staff texted or emailed and called again and sent a reminder letter (see letters and text/email reminder scripts).

Should a subject prefer to return the materials in person, rather than by having USPS/UPS pick up study materials from their home, study staff offered to meet with Veteran in-person at the VA in a clinical setting for a face-to-face visit in order to hand off the materials. All VA policies with regard to masking and distancing during the SARS-CoV-2 pandemic were followed during this interaction. This option was also offered to enrolled study subjects for all follow-up assessments and visits. Staff were sure to confirm identity of the participant prior to interacting and in a private location to protect the identity of the individual.

**Randomization and group logistics (~15 minutes).** Participants who completed verbal consent and baseline measures were randomized to either *MOVE!* (control) or *MOVE!+UP* (intervention). Those randomly assigned to the control condition were scheduled directly into *MOVE!* VVC, and we made reminder calls and sent letters to promote attendance of initial sessions (see ALT Letters and Phone/text Scripts). Those

randomized to *MOVE!+UP* were instructed to not participate in *MOVE!* during the study. Study staff went over the details of group session dates/times and how to access the respective VVC groups and will walk randomized participants through that process. They were reminded that a participant manual would be sent to them for *MOVE!+UP* or *MOVE!* in the mail prior to the group sessions start. *MOVE!+UP* participants were encouraged by study staff to map out a safe and pleasant walking route using the audit that sent to them with their manual before their first session (see ALT Walking Audit).

**Follow-up assessments (30-60 minutes)** The 16-week satisfaction questionnaire tailored for *MOVE!+UP* and *MOVE!*, was mailed to be completed on hard copy, or emailed with a personalized Qualtrics URL link to be completed electronically, to participants at approximately 15 weeks so they could complete and/or return it in a postage-paid, pre-addressed envelope at approximately 16 weeks. If the survey was not received, staff contacted the subjects via phone to obtain the 16-week data. Participants received follow-up reminder letters, emails, or phone calls if the 16-week assessment had not been completed. If subjects did not return the measure via mail or complete the measure via the emailed personal link, they had the option to complete the assessment via phone. The measure assesses 30 *MOVE!+UP* content and structure features with a Likert satisfaction scale, with space for Veterans to suggest changes for each. We modified that measure to remove the specific *MOVE!+UP* domains to assess *MOVE!* satisfaction among control participants. We sent emails to individual participants only one email at a time (rather than blind carbon copy) to avoid disclosing the email addresses of other consented subjects.

**The 6-month assessments** mirror the baseline assessment procedures. The various components of the follow-up assessment visits could be completed on different dates as needed (as long as all components are completed within the acceptable assessment visit window) to best accommodate Veterans. Ideally, all components would be completed on the same day during the same VVC visit. Ideally the subject would show their study issue scale readout to staff during the VVC session. If this is not possible, they may take a photo of the scale reading with their cell phone and text it to a staff member's GFE iPhone. This allows for the message to be encrypted. Staff do not text the Veteran back. This will only be done in the rare circumstance that the scale cannot be visualized.

**12-month follow-up assessment (15-30 minutes).** At the final assessment visit at 12 months, all participants have a final weight measurement taken. PTSD symptomology, non-VA utilization, Adverse Events, and pregnancy will also be recorded at this time. All participants will be thanked for their participation in the study. This visit takes place

via VVC (or other approved video conferencing modality should VVC not be working).

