**Note: Aim 3 analyses are not covered in this statistical analysis plan.**

Table 1. Statistical Models

Analysis	Outcome(s)	Independent Variables
Primary analysis	6-month absolute weight change from baseline (pounds)	Binary treatment indicator  Baseline weight  Binary African-American race indicator
Secondary analyses	1. 6-month absolute change in PTSD symptoms from baseline 2. 12-month absolute change in PTSD symptoms from baseline 3. 12-month absolute weight change from baseline (pounds)	Binary treatment indicator  Baseline outcome  Binary African-American indicator (weight analysis only)
Exploratory analyses	6-month absolute change from baseline in: 
 
Diet quality
 
Eating habits
 
Night eating
 
Emotional eating
 
Average MVPA and average LMVPA (adjust for total # of valid days at baseline and 6 months)
 
Social support – Diet
 
Social discouragement – Diet
 
Social support – physical activity
 
Social discouragement – physical activity
 
Insomnia Severity Index (ISI)
 
Depression symptoms
 
Internalized Weight Bias
 
	Binary treatment indicator  Baseline outcome

 All models account for clustering through the inclusion of a random intercept for group treatment cluster.

Analysis	Outcome(s)	Independent Variables
Exploratory Analyses	Binge eating at 6 months	Binary treatment indicator
Sensitivity analyses:  adjusting for prior weight loss treatment	1. 6-month absolute weight change from baseline (pounds) 2. 12-month absolute weight change from baseline (pounds)	Binary treatment indicator  Baseline outcome  Binary African-American indicator  Total number of MOVE! visits 12 months prior to baseline  Binary indicator of prescription weight loss medications at baseline
Sensitivity analyses:  adjusting for prior mental health treatment	1. 6-month absolute change in PTSD symptoms from baseline 2. 12-month absolute change in PTSD symptoms from baseline	Binary treatment indicator  Baseline outcome  Total number of mental health visits 12 months prior to baseline, per EHR  Number of PTSD visits in the prior year  Binary indicator of PTSD medications in the last year

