Participants bear no financial risk from any adverse effects of encounters from this study. Primary Care Provider (or other VA physician) approval was obtained before enrollment into the intervention or control condition of the study, and participants were engaged in PTSD care, which facilitated care coordination for medical and mental health issues that arose. For recruitment mailings to prospective participants, they were made via an introductory letter with a stamped postcard allowing them to opt out of further contact by the study team thus limiting risk for invasion of privacy. Participants completed assessment measures via VVC (or other approved video conferencing modality should VVC not be working) or over the phone. However, accelerometers were collected via mail in the pre-packaged envelope that only includes their subject ID and no identifiers. Study staff reminded the participants to remove the accelerometer and arranged for UPS to pick up the accelerometer return envelope directly from the participant or for them to be returned by mail.

The safety procedures for the *MOVE!+UP* community walk are detailed earlier, including the pre-walk audit for a safe route.

b. VA Employees (Aim 3)

Interviews with employees will be conducted via Webex for Business, the method now encouraged by VA. Interviews will be transcribed, with individually identifiable information redacted and stored separately from unique subject identifiers. Aside from for recruitment purposes, no identifying information will be needed for research involving VA staff. We will ensure that all VA staff participants understand they will be assigned a unique study ID that will be used to label all study data such that data could not be linked to individuals.

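### The accelerometer baseline week appears to follow disclosure of arm for at least some participants, and the activity models also adjust for 6-month wear days; either can bias two exploratory estimates

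*Combined protocol and SAP*

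**What the plan says.** Section 5.5 gives the order of enrolment. Under Orientation content, participants consent, complete baseline measures, and then: "They were then randomized, and notified of their assignment and details/logistics". The next paragraph, on exploratory measures and the accelerometer, has the device worn "for one week following the baseline visit". It also explains a change made from cohort 2: "To ensure that all exploratory behavioral and psychological measures were collected prior to randomization, study staff administered the questionnaire during the virtual visit". No matching step is described for the accelerometer, and an occasional repeat wear is allowed when data are invalid or the device is not returned.

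Randomization and group logistics, a step of about 15 minutes, states the condition for allocation: "Participants who completed verbal consent and baseline measures were randomized to either" arm. After allocation, in MOVE!+UP, "participants were encouraged by study staff to map out a safe and pleasant walking route". Controls are booked into MOVE! video groups and receive reminder calls and letters.

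On physician approval, the Phone screen subsection says that staff confirmed it "following the screening and eligibility visit, so it was possible someone's physician could disallow participation after they've provided verbal consent", and Section 7.0 says that "approval was obtained before enrollment into the intervention or control condition of the study".

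Section 5.6.b applies the primary-outcome model to all continuous outcomes: 6-month change regressed on arm and the baseline value, with a random intercept for treatment group. Its table of statistical models lists, among the exploratory outcomes, "Average MVPA and average LMVPA (adjust for total # of valid days at baseline and 6 months".

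**The concern.** A baseline covariate is safe in a randomised comparison because allocation cannot have affected it. If participants already knew their arm when they wore the device, that protection is lost. Any arm difference in activity during that week is carried into the treatment estimate through the baseline term. The arms were also prompted differently after allocation, with the walking-route task given to MOVE!+UP only.

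The second problem does not depend on timing. Valid days at 6 months are measured after randomisation whatever the date of baseline wear. If arm affects how many days people wear the device, and wear shares causes with activity, conditioning on it distorts the comparison.

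What is at stake is the reading of Aim 2. Table 5 treats accelerometry as the gold standard for physical activity, a named treatment target meant to help explain the weight result. A distorted activity estimate could mislead that explanation.

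**Working it through.** **Plan's own figures.** The plan gives no power, effect size or SD for accelerometry. Its one sample-size figure, for weight, reproduces: 2 x (13 x (1.960 + 1.282) / 8.4)^2 = 50.33 per arm; x 1.21 for clustering (1 + 7 x 0.03) and / 0.75 for attrition = 81.2, so 82 per arm and 164 in total. This point leaves it unchanged.

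**Timing, side by side.** For wear after disclosure: Section 5.5 puts notification of arm directly after baseline measures, wear starts after the visit, all visit components are ideally done on one day, and repeat wear would fall later still. For some wear before allocation: baseline measures had to be complete before randomisation, without saying whether the wear week counts; approval came after the visit but before arm entry; visit components could fall on different dates; and 5 of 179 enrolled were not randomised (179 - 174). No section states wear dates relative to randomisation.

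**Bias from a post-allocation baseline.** Let r be the slope of 6-month activity on baseline activity and d the arm difference (MOVE!+UP minus control) in the baseline week caused by knowing the arm, in SD units. With the baseline as covariate, modelling change or modelling the 6-month value gives the same arm coefficient, so

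bias = -r x d.

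Both inputs are assumptions:

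| r | d = 0 | d = 0.1 | d = 0.2 | d = 0.3 |
|---|---|---|---|---|
| 0.3 | 0 | -0.03 | -0.06 | -0.09 |
| 0.5 | 0 | -0.05 | -0.10 | -0.15 |
| 0.7 | 0 | -0.07 | -0.14 | -0.21 |

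If controls raise activity more, d is negative and the signs reverse.

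**In minutes, as an assumed illustration.** One extra 30-minute walk in the week is 30/7 = 4.3 min/day. With r of 0.5 to 0.7 the shift is 2.1 to 3.0 min/day. (Section 5.6.a gives the walk as 40 minutes, against 30 in Section 5.1; the two need reconciling. At 40 minutes: 40/7 = 5.7, giving 2.9 to 4.0.) The only activity change in the documents is pilot cohort 5's 290.0 (SD 611.2) minutes a week, from 8 Veterans with no instrument stated: 41 (SD 87) min/day. Against that rough yardstick, 2.1 to 3.0 min/day is about 5 to 7% of the pilot change, or 0.02 to 0.03 SD. One such walk would be d = 4.3/87 = 0.05, below the range in the table.

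**Bias from adjusting for 6-month valid days.** Suppose arm shifts valid days by a SD, valid days correlate g with an unmeasured factor, and that factor has effect 0.4 SD on activity. Then

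bias = -0.4 x a x g.

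For a = 0.25 and g = 0.3 this is -0.03; for a = 0.5 and g = 0.5 it is -0.10. It is zero if a or g is zero, and positive if arm lowers wear. Again all inputs are assumed.

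Simulation with 1,000,000 records per scenario agreed with both formulas to within 0.002.

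**Cost of omitting baseline.** On standardised values, adjustment lowers the variance by r^2 x 2/n and adds squared bias r^2 x d^2. It therefore has the lower mean squared error unless |d| exceeds sqrt(2/n). With 174 randomised and 25% attrition, n = 174 x 0.75 / 2 = 65 per arm and sqrt(2/65) = 0.18 SD, ignoring clustering.

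**The case against.** The strongest reply is that the timing is inferred from the order of the text. The stated aim was to collect all exploratory measures before randomisation, allocation required completed baseline measures, and approval came after the visit, so some participants may have worn the device before allocation. This stands: a reader might infer that every baseline week followed disclosure, but the documents do not say so. They also do not say that any wear week finished first.

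A reader might also infer that the activity effect is biased toward no difference. That is not supported. The route audit was mailed with the manual before the first session, and nothing shows it arrived in the wear week. Programme walks take place during sessions. Controls were prompted too, and an early change among them would push the estimate the other way.

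Nor do the documents support extending the point to the main results. Baseline weight and the PCL-5 were taken at the eligibility step, before randomisation.

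Two cautions about remedies also stand. A minimum-valid-day rule at 6 months conditions on the same post-randomisation variable by excluding people, so it is no substitute for the covariate. And below a baseline-week difference of about 0.18 SD, baseline adjustment is the better estimator on mean squared error, so there is no case for demoting the adjusted model outright.

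None of this answers the adjustment for 6-month valid days, which the plan states plainly.

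**Conclusion.** The concern holds in a limited form. On the natural reading, the accelerometer baseline follows disclosure of arm for at least some participants, and the models treat it as pre-treatment. They also condition on a post-randomisation wear count. Either can bias the MVPA and LMVPA estimates; neither is shown to do so. Over the assumed inputs the shifts are -0.03 to -0.21 SD and -0.03 to -0.10 SD, with opposite signs possible, and each is zero if the arms do not differ on the quantity concerned. The one-walk illustration falls at or below the low end of the first range. The real size is unknown until the dates and the baseline-week difference are examined. The scope is two exploratory Aim 2 outcomes.

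**What to change.** 1. Remove valid days at 6 months as a covariate for MVPA and LMVPA. The outcome is already an average, so the day count is not needed to put people on a common scale.
2. State in Section 5.5 when the wear week fell relative to randomisation, reconciling it with the approval and completed-baseline wording. Compare randomisation and wear dates, including repeat wears, and report the between-arm difference in the baseline week.
3. Where wear followed allocation, pre-specify a sensitivity analysis of the 6-month activity value that omits the post-allocation baseline and baseline valid days, and read the baseline-adjusted result in its light. Where wear came first, keep the adjustment and say so.

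Cohort 1 questionnaires, which were mailed back, need the same treatment only if their dates show completion after randomisation; Section 5.5 reports only that some were lost.

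The cost is SAP wording, a date check on data that should already be held, a little more analysis, and wider intervals in the sensitivity analysis. Follow-up appears complete, since the SAP already reports that nobody had bariatric surgery during the study. The Abstract reports no findings yet, so the wording should be settled before activity is analysed by arm.
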